## **12.9. Pregnancy**

Patients who are not of childbearing potential due to being postmenopausal (2 years without menstruation) or surgical sterilisation (oophorectomy, hysterectomy and/or tubal ligation) do not need to use contraception to be eligible for the trial. All other patients are considered to be of childbearing potential.

Women of childbearing potential and sexually active men must use highly effective contraception during treatment with nivolumab and ipilimumab and until 12 months thereafter. Please refer to section 10.10 for highly effective contraception methods.

In the case of pregnancy occurring during the course of the trial or within 12 month after treatment discontinuation, the investigator shall immediately (within 24 hours after awareness of pregnancy) notify ETOP by completing the pregnancy form in ETOPdata in accordance with the SAE reporting procedures. Follow-up information regarding the course of the pregnancy, including perinatal and neonatal outcome and, where applicable, offspring information must be reported (within 14 days) on the Pregnancy Form in ETOPdata.

Any pregnancy that occurs in a female partner of a male study participant should be reported to ETOP. Information on this pregnancy will be collected on the Pregnancy Form.

## 13. Response evaluation

### 13.1. RECIST 1.1 criteria

The patient's response to chemo-radiotherapy treatment and to nivolumab plus ipilimumab consolidation treatment will be assessed by RECIST 1.1 criteria (see appendix 2). Only patients with stable or responding disease will be eligible for randomisation. The response assessment according to RECIST 1.1 should be done by the local radiologist and reported on the eCRF.

For exploratory purposes, the response in the randomised nivolumab plus ipilimumab consolidation phase of the trial will also be assessed post-hoc centrally by immune-related response criteria based on RECIST 1.1.

### 13.2. CT Schedule for tumour assessment

#### Before randomisation:

At baseline: brain MRI (or contrast enhanced CT of the brain), and whole body FDG-PET CT including a contrast-enhanced CT of thorax and upper abdomen (incl. liver, kidney, adrenals). If FDG-PET CT is not available, contrast enhanced CT of the thorax and upper abdomen (incl. liver, kidney, adrenals) and bone scan is required for tumour assessment at baseline.

Within 14 days prior to randomisation: contrast-enhanced CT of thorax and upper abdomen (incl. liver, kidney, adrenals)

#### After randomisation:

For both treatment arms, post randomisation CT scans of thorax and upper abdomen will be repeated according to the schedule indicated below, until tumour progression:

- up to 18 months: every 9 weeks 9, 18, 27, 36, 45, 54, 63, 72, 81 (+/- 1 week)
- up to 2 years: every 12 weeks 93, 105 (+/- 1 week)
- years 3 and 4: every 6 months (26 weeks) 131, 157, 183, 209 (+/- 1 week)
- at 5 years: 260 (+/- 1 week)

### 13.3. Determination of time point response

**Table 15: Determination of time point response**

Target lesions	Non-target lesions	New lesions	Overall response
CR	CR	No	CR
CR	Non-CR / non-PD	No	PR
CR	Not evaluated	No	PR
PR	Non-PD or not all evaluated	No	PR
SD	Non-PD or not all evaluated	No	SD

Target lesions	Non-target lesions	New lesions	Overall response
Not all evaluated	Non-PD	No	NE unless the sum of diam. of evaluated lesions in- dicates PD 
PD	Any	Yes or no	PD
Any	PD	Yes or no	PD
Any	Any	Yes	PD

- 1) From ref. 1 in appendix 2, p.234: When no imaging/measurement is done at all at a particular time point, the patient is not evaluable (NE) at that time point. If only a subset of lesion measurements are made at an assessment, usually the case is also considered NE at that time point, unless a convincing argument can be made that the contribution of the individual missing lesion(s) would not change the assigned time point response. This would be most likely to happen in the case of PD. For example, if a patient had a baseline sum of 50 mm with 3 measured lesions and at follow-up only 2 lesions were assessed, but those gave a sum of 80 mm, the patient will have achieved PD status, regardless of the contribution of the missing lesion.

### 13.4. Determination of best overall response

Best overall response is defined as best response across all time points. Confirmation of partial or complete response by an additional scan is not requested in this trial.

### 13.5. Storage of imaging

All CT, FDG-PET-CT scans and MRI images must be stored locally in electronic format for later central review, please consult the *STIMULI procedures manual* for detail.

## 14. Endpoints definition

### 14.1. Progression-free survival

It is defined as the time from the date of randomisation until documented progression or death, if progression is not documented. Censoring will occur at the last tumour assessment only if patient is lost to follow-up.

### 14.2. Overall survival

Defined as time from the date of randomisation until death from any cause. Censoring will occur at the last follow-up date.

### 14.3. Objective response

Objective response is defined as best overall response (CR or PR) across all assessment time-points during the period from randomisation to termination of trial treatment. Objective response to chemo-radiotherapy will be determined by tumour assessment around week 15 (see trial schedule in section 2).

Objective response to IMP treatment will be determined using RECIST 1.1 criteria (see section 13).

[figure not shown]

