Before PD: Patients who completed consolidation treatment (in the observation arm this corresponds to 15 months after randomisation) or discontinued IMP treatment before tumour progression should have physical examination at regular intervals (blood pressure, performance status and weight). In the first 18 months after randomisation this has to be done together with the CT scans according to the schedule indicated in footnote 13, then every 12 (+/- 1) weeks until PD for a maximum of 4.5 years after the enrolment of the last patient.  
After PD: Patients with tumour progression will end trial treatment and should have documented survival, and further lines of treatment every 12 weeks (+/-1 week) starting from date of progression during the first year after randomisation, then every 6 months (+/- 4 weeks) up to 4.5 years after the enrolment of the last patient.
- 9 **Haematology:** haemoglobin, platelets, complete white blood cell count [leucocytes, neutrophils, eosinophils, basophils (or total granulocytes), lymphocytes, monocytes]
- 10 **Only patients in experimental arm.** In case of abnormal TSH value, also free T3 and T4 has to be measured.
- 11 **Pregnancy test:** Women of childbearing potential, including women who had their last menstrual period in the last 2 years, must have a negative serum or urine pregnancy test within 7 days before beginning of chemotherapy. The test has to be repeated within 7 days before randomization and then every 6 weeks during consolidation treatment. Pregnancy tests should be repeated at approximately 30 days and approximately 70 days after consolidation treatment stop.
- 12 **Tumour assessments before randomisation**  
At baseline: brain MRI (or contrast enhanced CT of the brain), *AND* whole body FDG-PET CT including a contrast-enhanced CT of thorax and upper abdomen (incl. liver, kidney, adrenals). If FDG-PET CT is not available, contrast enhanced CT of the thorax and upper abdomen (incl. liver, kidney, adrenals) and bone scan is required for tumour assessment at baseline.  
Within 14 days prior to randomisation: contrast-enhanced CT of thorax and upper abdomen (incl. liver, kidney, adrenals)
- 13 **Tumour assessments after randomisation**  
 For both treatment arms, CT of thorax and upper abdomen (incl. liver, kidney, adrenals) have to be done as indicated below:
- |                           |                           |                            |  |

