#### b) Maintenance:

Nivolumab at a dose of 240 mg i.v. over a period of 30 minutes, once every 2 weeks (+/- 2 days, without dosing delay) for maximum 12 months from start of maintenance phase. The first dose of maintenance nivolumab will be administered 3 weeks after the last IMP doses of induction phase

Upon disease progression or completion of trial treatment, further therapy will be at the discretion of the treating physician.

16.1.4. **End of treatment:** an end of treatment visit will occur within 30 days following the last administered dose of trial treatment. For patients in the observation arm the end of treatment visit is to be scheduled within 30 days following PD or 15 months after randomisation. For patients who have not been randomised the end of treatment visit is to be scheduled within 30 days following PD or within 30 days following the last chemotherapy cycle.

16.1.5. **Follow-up period**

16.1.5.1. Before tumour progression: In the first 18 months after randomisation follow-up visits will occur together with the CT scans according to the schedule indicated in section 13.2, then every 12 (+/- 1) weeks until PD for a maximum of 4.5 years after the enrolment of the last patient.

16.1.5.2. After tumour progression: follow-up visits will occur every 12 weeks in the first year after randomisation starting from date of progression, then every 6 months up to 4.5 years after the enrolment of the last patient. This applies also to patients who have been enrolled but not randomised (see section 18.4).

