## **16.9. Evaluations in the follow-up phase before progression**

Patients who completed consolidation treatment (this corresponds to 15 months after randomisation in the observation arm) or discontinue IMP treatment before progression should have a regular physical examination (blood pressure, performance status and weight). In the first 18 months after randomisation this has to be done together with the CT scans according to the schedule below, then every 12 (+/- 1) weeks until PD or up to 4.5 years after the enrolment of the last patient.

For both treatment arms, post randomisation CT scans of thorax and upper abdomen will be repeated according to the schedule indicated below, until tumour progression:

- up to 18 months:	every 9 weeks	9, 18, 27, 36, 45, 54, 63, 72, 81 (+/- 1 week)
- up to 2 years:	every 12 weeks	93, 105 (+/- 1 week)
- years 3 and 4:	every 6 months (26 weeks)	131, 157, 183, 209 (+/- 1 week)
- at 5 years:		260 (+/- 1 week)

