2.2.2 Secondary endpoints

Secondary endpoints include OS, ORR, TTF and adverse events (AEs) graded according to CTCAE v4.0. More specifically:

- OS is defined as the time from the date of randomization until death from any cause.
 Censoring (patients without death) for OS will occur at the last follow-up date.
- ORR is defined as the rate of best overall response (complete or partial response)
 according to RECIST 1.1 criteria across all assessment time-points, during the period from
 randomization to termination of trial treatment. Of note, the determination of ORR will be
 restricted to patients who have not attained a CR during chemo-radiotherapy.
- TTF is defined as the time from the date of randomization to treatment failure for any reason (including progression of disease, treatment toxicity, refusal, lost to follow-up and death). Censoring for TTF (patients without failure) will occur at the last-follow-up date.
- Toxicity, defined as adverse events classified according to CTCAE v4.0.

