2.3 Analysis population

Efficacy cohort: The efficacy cohort is the Intention-to-treat (ITT) population of the trial and includes all randomized subjects under protocol AM1. Patients will be evaluated in the treatment arms to which they were randomly assigned, regardless of the treatment actually received, including patients who were randomized but did not receive any trial treatment.

Safety cohort: The safety cohort consists of all subjects who have received at least one dose of IMP treatment plus all patients randomized to observation arm (under protocol AM1).

Patients will be evaluated according to the treatment they actually received, irrespective of their allocated treatment at randomization.

Per-Protocol cohort: Per-protocol cohort includes all patients enrolled under protocol AM1.

Per-Protocol safety cohort: Per-protocol safety cohort includes all patients enrolled under protocol AM1, who received at least one dose of chemo-radiotherapy after enrollment.

3 Primary efficacy analysis of PFS

Primary efficacy analysis of PFS (primary endpoint) will be performed on **all randomized patients under AM1 protocol, based on their initial treatment assignment (ITT, efficacy cohort)**. PFS time is measured from time of randomization.

Formal hypothesis testing

Based on the protocol AM1 and after the modifications arose from the premature study accrual termination, the trial is designed to test the hypotheses that treatment with chemoradiotherapy and PCI followed by consolidation treatment (nivolumab plus ipilimumab) will lead to an increase in median PFS to 22.8 months, from 13.1 months under treatment with chemoradiotherapy and PCI without consolidation treatment. According to the study design, this corresponds to a PFS HR of 0.57. Using 80% power and a one-sided type I error of 5%, a total of 81 PFS events are needed to observed in order to achieve the trial goal.

In the frame of final efficacy analysis, the **formal comparison** of the PFS between the two treatment arms, will be based on **stratified log-rank test** (with number of fractions of radiotherapy [1/2] and administration of FDG-PET-CT [Yes/No] being the stratification factors). Unstratified log-rank test will be also calculated. This would be of particular value in case at least one stratum level has very low number of patients.

Further PFS analyses

The following **PFS analyses** will also be performed and presented

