4.3.3 Objective response rate

- Overall best responses and objective response rate (ORR) will be presented overall and separately for the two treatment arms, along with a 95% exact binomial CI. ORR will be compared between the two treatment groups using Fisher's exact test and Cochran-Mantel-Haenszel test stratified by the stratification factors of the trial.
- Logistic regression models will be further applied to investigate the treatment effect on ORR, adjusting for stratification factors and variables of clinical interest.
- Note: ORR will be calculated based on the randomized patients who have not attained complete response during chemo-radio therapy.

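### The ORR window ends when trial treatment ends, so experimental patients who stop early without progression, or never start, are assessed for response over a shorter period than progression-free observation patients

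*Protocol*

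**What the plan says.** Protocol 14.3 defines objective response as the best response (CR or PR) "across all assessment time-points during the period from randomisation to termination of trial treatment". SAP 2.2.2 repeats the rule: the period runs from "randomization to termination of trial treatment". Protocol 13.4 takes the best response over every assessment and sets no end tied to treatment.

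The observation arm receives no treatment after randomisation. Elsewhere the protocol gives that arm a stand-in for the end of treatment. For completed consolidation, the trial schedule (footnote 8) says "in the observation arm this corresponds to 15 months after randomisation", and section 16.9 says "this corresponds to 15 months after randomisation in the observation arm". For experimental patients, section 16.1.4 states that "an end of treatment visit will occur within 30 days following the last administered dose of trial treatment"; sections 16.1.4 and 16.8 time the observation arm's visit from progression or 15 months. None of these places mentions ORR.

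Protocol 13.2 and 16.9 put both arms on one CT schedule until progression, whether or not treatment has stopped. Footnote 13 of the trial schedule and section 16.8.7 also ask for a CT at discontinuation without progression, unless one was done recently.

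The efficacy cohort in SAP 2.3 is all patients randomised under amendment 1, "including patients who were randomized but did not receive any trial treatment". Under SAP 4.3.3, "ORR will be calculated based on the randomized patients who have not attained complete response during chemo-radio therapy", and "ORR will be compared between the two treatment groups using Fisher's exact test", a stratified Cochran-Mantel-Haenszel (CMH) test and logistic regression.

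**The concern.** In the experimental arm the end of the response window depends on what happens to the patient after randomisation: toxicity, refusal, or never starting. In the observation arm it either has no literal meaning or, on the borrowed equivalent, depends only on progression or a fixed 15 months. The denominator does not shrink to match, because early stoppers and never-treated patients remain in it.

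A response first seen after early stopping is therefore not counted, while a response at the same week in a progression-free observation patient is. That is unequal ascertainment in a planned between-arm comparison. The protocol gives reason to expect some late responses: section 10.11 says immune activation may take weeks to months to show. The likely direction is understatement of experimental ORR. Duration of response is touched as well if its responders are taken from the same window. SAP 2.2.3 does not tie it to one.

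**Working it through.** The documents give no target, power or assumed rate for ORR, so there is no plan figure to reproduce. The check counts scheduled CTs inside each window.

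**Inputs.** First dose 0–14 days after randomisation; four induction doses 21 days apart; maintenance starts 21 days after dose 4 and lasts at most 12 months (Protocol 10.6). CTs at weeks 9, 18, 27, 36, 45, 54, 63, 72, 81, each ±1 week (Protocol 13.2). Delayed doses are postponed, not skipped, with delays up to 6 weeks (10.7.3).

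**Completers.** Maintenance starts on day 84–98. Adding 12 months gives about 14.8–15.2 months. For observation, 15 months = 65.2 weeks. Both contain the CTs at weeks 9 to 63, which is 7.

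**Early stoppers without progression.** CT windows in days: week 9 = 56–70, week 18 = 119–133, week 27 = 182–196, week 36 = 245–259. The delayed rows take the latest possible start and a 42-day delay before every later dose.

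| Last dose | 1 | 2 | 3 | 4 |
|---|---|---|---|---|
| Undelayed, day | 0–14 | 21–35 | 42–56 | 63–77 |
| Scheduled CTs by last dose | 0 | 0 | 0–1 | 0–1 |
| Scheduled CTs by last dose + 30 days | 0 | 0–1 | 1 | 1 |
| Maximally delayed, latest day | 14 | 77 | 140 | 203 |
| Most scheduled CTs by then | 0 | 1 | 2 | 3 |

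Adding 30 days to the delayed rows (44, 107, 170, 233) leaves the maxima at 0, 1, 2, 3. Interruptions beyond 6 weeks, allowed by exception, are not counted. A patient who never starts has none. A progression-free observation patient has 7 on the 15-month reading.

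**Illustrative size.** Let s be the share of the experimental denominator that stops early without progression or never starts, and r the share of those whose first response falls after the window closes. Understatement in points = 100 × s × r. The documents do not give r; 0, 5, 10 and 20% are assumed.

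- s = 11% (Protocol 11.2.2, same induction doses in SCLC, treatment-related stops only): 0, 0.6, 1.1, 2.2 points.
- s = 36.4% (Protocol 11.3, melanoma): 0, 1.8, 3.6, 7.3 points.

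Neither s is this trial's rate. The first comes from an interim lock with 43% still on treatment. The second covers stopping at any time, including late stoppers who would already have had several scans.

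**Sampling error.** At an assumed ORR of 20% in each arm, the 95% half-width of the difference is 1.96 × √(2 × 0.2 × 0.8 / n). With the planned 260 / 2 = 130 per arm this is 9.7 points. SAP 1.4.2 reports early closure with fewer randomised but gives no number. For an assumed 100 or 60 per arm the half-width is 11.1 or 14.3 points. Excluding patients with a prior CR widens it further.

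**The case against.** The best defence is that on-treatment response is a recognised choice, and that the discontinuation CT gives most early stoppers a scan at or near the end of their window. Much of this stands. The counts above cover scheduled CTs only, so a reader might infer that early stoppers are never assessed; the documents do not support that. What remains is responses first seen after the discontinuation scan, patients who never start, and the absence of any statement that this scan counts.

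A reader might also infer that collected scans are discarded only in the experimental arm. That is not so. With a 15-month end, progression-free observation patients and experimental completers also lose every scan from week 72 on. The difference lies in when the window closes.

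Third, the contrast with seven CTs rests on passages about visits and follow-up. Read literally, the observation window has no end at all. This limits how firmly the gap can be stated, but it also shows that the definition needs repair.

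Finally, the direction need not be uniform. Protocol 10.11.1 lets some experimental patients continue beyond week-9 progression, which could carry a treatment-based window past progression in that arm only. This could partly offset the understatement, and a common window removes it too.

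**Conclusion.** The point holds as a small, inexpensive correction to a secondary endpoint. Protocol 14.3 and SAP 2.2.2 conflict with Protocol 13.4, give the observation arm no usable end date, and shorten response ascertainment for experimental patients who stop early without progression or never start. The arms match only for treatment completers, and that match assumes the progression-or-15-months equivalent applies to ORR.

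The expected direction is understatement of experimental ORR in the Fisher, CMH and logistic comparisons. The size is not known. The 0 to 7.3 point range rests on an assumed r and on discontinuation rates from other trials, and it starts at no effect. Even its top is below the 9.7-point half-width at the planned size, and fewer patients than planned were randomised. A reader might infer that the ORR comparison is badly distorted or that the trial's conclusion is at risk. The documents support neither: no bias of a given size can be derived from them, and the primary PFS analysis does not use this window.

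**What to change.** Reconcile Protocol 13.4 and 14.3 with SAP 2.2.2 and 4.3.3. Define best overall response identically in both arms, from randomisation to the first of RECIST 1.1 progression, death or start of new anticancer therapy, regardless of whether trial treatment was stopped early or never started. A 15-month cap in both arms is optional. It should not replace the stop at new therapy, because responses to later treatment could then be credited to the randomised arm.

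State that responders for duration of response come from the same window. Keep the on-treatment version as a sensitivity analysis, with the observation arm ending at progression or 15 months and the discontinuation CT counted.

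The cost is SAP wording, a documented change to the 14.3 definition, and possibly data queries for dates of new therapy begun before progression. The CTs are already scheduled in both arms, so no imaging is added.

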### 14.4. Time to treatment failure

Defined as time from the date of randomisation to discontinuation of treatment for any reason (including progression of disease, treatment toxicity, refusal and death). Censoring will occur at the last follow-up date.

### 14.5. Toxicity

Adverse events classified according to NCI CTCAE Version 4.

## 15. Biological material and translational research

### 15.1. Mandatory evaluations

Serum levels of TNF  $\alpha/\beta$  and IL6, and circulating antibodies will be determined centrally in every patient from samples taken prior to or at enrolment, at the time of randomisation, 9 and 18 weeks (+/- 3 days) after randomisation and at the time of progression.

